5.6.2 Restricted Medications and/or Procedures

Participants receiving maximally tolerated lipid-modifying therapy (other than PCSK9-targeted therapies) as described in Section 4.1 should be on a stable dose for at least 8 weeks prior to Screening (Visit 1). Participants taking PCSK9-targeted therapies (except for inclisiran) should have received at least 4 doses prior to Screening (Visit 1). Participants taking inclisiran must have received at least 2 stable doses prior to Screening (Visit 1). There should be no planned medication or dose changes of lipid-modifying therapy during study participation. Participants must agree not to initiate any new lipid-modifying medications (including supplements) and not to change the dose of the existing lipid-modifying medications (including supplements) during study participation. However, if there are changes to lipid-modifying therapy during the study, these data will be recorded and reported as a protocol deviation.

Participants are not required to be taking statins. Reasons for not using statin therapy must be documented as described in Section 5.6.3.

5.6.3 Documentation of Prior and Concomitant Medication Use

Any prior lipid-modifying therapies, administered at any time, must be recorded. Any non-lipid-modifying medications administered within 90 days prior to the first dose of study drug must be recorded. All prior and concomitant medications must be documented in the source documents and applicable eCRFs. Concomitant medications will continue to be assessed and recorded at every study visit from the time of informed consent until study participation is complete.

Data from all participants regarding lipid-modifying medications taken throughout the study will be recorded. The number of participants taking a statin or PCSK9-targeted therapy during the study and the number of participants who discontinue background statin therapy, along with the reasons for discontinuation of background statin therapy, will be recorded in the applicable eCRFs.

A participant's maximally tolerated stable statin dose will be determined by the Investigator using his/her medical judgment and available sources, including the participant's self-reported history of lipid-modifying therapy, for at least 8 weeks prior to Screening (Visit 1), and recorded in the applicable eCRFs.

No more than approximately 10% of participants in this study will be completely statin intolerant. For any participant not taking statin therapy due to statin intolerance (as defined in Inclusion Criterion 4), including those participants taking bempedoic acid or fibrate monotherapy, written confirmation will be required of both the participant and the Investigator stating that the participant is statin intolerant, aware of the benefit of statins to reduce the risk of a MACE, and aware that many other patients who are unable to tolerate a statin were actually able to tolerate a different statin or dose. Statin intolerance should be recorded as intolerance to any dose of any statin as historical events attributed to the statin in question, in the source documentation and eCRF as part of the medical history to confirm intolerance to statins.²⁵

Documentation in the eCRF of the reason why a participant is unable to take HIS is required.

5.6.4 Dietary Guidelines

Participants will be instructed to follow a lipid-lowering diet as per local or regional guidelines throughout the study.

6 STUDY PROCEDURES

Study procedures will follow the Schedule of Procedures (Appendix A).

Unscheduled visits may be scheduled as needed per the judgment of the Investigator. Procedures will be determined based on the reason for the visit.

7 EFFICACY AND PHARMACOKINETIC ASSESSMENTS

7.1 Efficacy Assessments

7.1.1 Efficacy Endpoints

7.1.1.1 Primary efficacy endpoint

The primary efficacy endpoint is the percent change from Day 1 to Day 84 in LDL-C. Co-primary endpoints include the percent change from Day 1 to Day 84 in LDL-C for the obicetrapib 10 mg + ezetimibe 10 mg FDC treatment group as follows:

- Compared with the placebo group;
- Compared with the ezetimibe 10 mg monotherapy treatment group; and
- Compared with the obicetrapib 10 mg monotherapy treatment group,

And the percent change from Day 1 to Day 84 in LDL-C for the obicetrapib 10 mg monotherapy treatment group compared with the placebo group.

7.1.1.2 Secondary efficacy endpoints

The secondary efficacy endpoints include the following, in hierarchical order:

- Percent change from Day 1 to Day 84 in non-HDL-C for the obicetrapib 10 mg + ezetimibe 10 mg FDC treatment group compared with the placebo group;
- Percent change from Day 1 to Day 84 in ApoB for the obicetrapib 10 mg + ezetimibe 10 mg FDC treatment group compared with the placebo group;
- Percent change from Day 1 to Day 84 in non-HDL-C for the obicetrapib 10 mg monotherapy treatment group compared with the placebo group;
- Percent change from Day 1 to Day 84 in ApoB for the obicetrapib 10 mg monotherapy treatment group compared with the placebo group;
- Percent change from Day 1 to Day 84 in non-HDL-C for the obicetrapib 10 mg + ezetimibe 10 mg FDC treatment group compared with the ezetimibe 10 mg monotherapy treatment group;
- Percent change from Day 1 to Day 84 in ApoB for the obicetrapib 10 mg + ezetimibe 10 mg FDC treatment group compared with the ezetimibe 10 mg monotherapy treatment group;
- Percent change from Day 1 to Day 84 in non-HDL-C for the obicetrapib 10 mg + ezetimibe 10 mg FDC treatment group compared with the obicetrapib 10 mg monotherapy treatment group; and
- Percent change from Day 1 to Day 84 in ApoB for the obicetrapib 10 mg + ezetimibe 10 mg FDC treatment group compared with the obicetrapib 10 mg monotherapy treatment group.

7.1.1.3 Exploratory efficacy endpoints

The exploratory efficacy endpoints include the following:

- Percent change from Day 1 to Day 84 in VLDL-C, HDL-C, TG, Lp(a), and sdLDL-C for the obicetrapib 10 mg + ezetimibe 10 mg FDC treatment group compared with the placebo group, ezetimibe 10 mg monotherapy treatment group, and obicetrapib 10 mg monotherapy treatment group, and for the obicetrapib 10 mg monotherapy treatment group compared with the placebo group;
- Percent change from Day 1 to Day 84 in particle numbers and size, as measured by NMR analysis, of LDL-C, HDL-C, and VLDL-C for the obicetrapib 10 mg + ezetimibe 10 mg FDC treatment group compared with the placebo group, ezetimibe 10 mg monotherapy treatment group, and obicetrapib 10 mg monotherapy treatment group, and for the obicetrapib 10 mg monotherapy treatment group compared with the placebo group;
- Proportion of participants at Day 84 that achieve LDL-C <100 mg/dL (<2.6 mmol/L), LDL-C <70 mg/dL (<1.8 mmol/L), and LDL-C <55 mg/dL (<1.4 mmol/L) for the obicetrapib 10 mg + ezetimibe 10 mg FDC treatment group compared with the placebo group, ezetimibe 10 mg monotherapy treatment group, and obicetrapib 10 mg monotherapy treatment group compared with the placebo group; and

- Percent change from Day 1 to Day 28 in LDL-C for the obicetrapib 10 mg + ezetimibe 10 mg FDC treatment group compared with the placebo group, ezetimibe 10 mg monotherapy treatment group, and obicetrapib 10 mg monotherapy treatment group, and for the obicetrapib 10 mg monotherapy treatment group compared with the placebo group.

7.1.2 Lipid Profile/Biomarkers

Blood samples for the lipid profile must be obtained under fasting conditions (ie, after the participant has fasted for a minimum of 8 hours) and before study drug administration. For the purposes of this study, fasting will be defined as nothing by mouth except water and any essential medications. If a participant is not fasting, the Investigator should reschedule the visit as soon as possible.

LDL-C level will be calculated using the Martin-Hopkins and Friedewald equations unless TG ≥400 mg/dL (≥4.5 mmol/L) or LDL-C ≤50 mg/dL (≤1.3 mmol/L); in both cases, LDL-C level will be measured directly by preparative ultracentrifugation, also referred to as beta quantification. Additionally, LDL-C will be measured by preparative ultracentrifugation at Visit 2 (Day 1), Visit 4 (Day 84), and, in cases of early discontinuation of study drug or study, at an EOT Visit, for all participants.

7.1.3 Lipoprotein (a)

A plasma sample for Lp(a) will be collected at visits specified in the Schedule of Procedures (Appendix A). Samples should be collected prior to study drug administration and while the participant is fasting (a minimum of 8 hours).

7.1.4 Nuclear Magnetic Resonance Analysis of Lipids

A plasma sample for NMR analysis will be collected at visits specified in the Schedule of Procedures (Appendix A). Samples should be collected prior to study drug administration and while the participant is fasting (a minimum of 8 hours).

7.1.5 Urine Albumin-Creatinine Ratio

A urine sample for urine albumin-creatinine ratio will be collected at visits specified in the Schedule of Procedures (Appendix A).

7.1.6 Serum Archive Samples for Future Assessment

Serum archive samples will be collected prior to the first dose at Visit 2 (Day 1) and at Visit 4 (Day 84) (or at an EOT Visit, in cases of early discontinuation of study drug or study) for potential future assessment of conditions associated with cholesterol metabolism. Samples should be collected prior to study drug administration and while the participant is fasting (a minimum of 8 hours). If the samples are analyzed, it will be for non-genetic tests.

7.2 Pharmacokinetic Assessments

Plasma obicetrapib and ezetimibe concentrations, both in combination and each as monotherapy, will be assessed at the scheduled PK collection times.

A PK sample will be collected prior to study drug administration for trough measurements of obicetrapib and ezetimibe in plasma. At Visit 2 (Day 1), Visit 3 (Day 28), Visit 4 (Day 84), and the EOT Visit, in cases of early discontinuation of study drug or study, participants should take study drug after a trough PK sample has been collected.

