4.5 Withdrawal Criteria

A participant may prematurely discontinue study drug and/or withdraw from the study at any time. However, a distinction must be made between premature discontinuation of study drug and withdrawal from the study. All efforts should be made to ensure the participant continues in the study per protocol. If a participant discontinues study drug prior to completion of the study, all efforts will be made to continue to follow the participant and collect data for all visits.

Only participants that request discontinuation from the study and withdraw consent will be considered withdrawn from the study. For safety reasons, it will be recommended that all participants who withdraw from the study complete an End of Treatment (EOT) Visit. Withdrawn participants will not be replaced.

Participants may need to discontinue study drug during the course of the study. All efforts will be made to restart the study drug; however, in the event of the following, participants may be permanently discontinued from study drug:

- Occurrence of any medical condition or circumstance that exposes the participant to substantial risk and/or does not allow the participant to adhere to the protocol-specified study drug treatment regimen;
- Any SAE, clinically significant AE, severe laboratory abnormality, intercurrent illness, or other medical condition, which indicates to the Investigator that continued treatment with study drug is not in the best interest of the participant;
- Pregnancy; or
- Requirement of prohibited concomitant medication.

If a participant permanently discontinues study drug, he/she will continue to participate in study visits as described below:

- If a participant discontinues study drug between Visit 2 (Day 1) and Visit 3 (Day 28) or at Visit 3 (Day 28), he/she should complete an EOT Visit at Day 28, return to complete Visit 4 (Day 84), and return to complete the Safety Follow-up Visit (Day 112); or
- If a participant discontinues study drug between Visit 3 (Day 28) and Visit 4 (Day 84), he/she should return for Visit 4 (Day 84) and the Safety Follow-up Visit (Day 112) as scheduled.

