5.5.4 Treatment Compliance

Compliance with the study drug regimen will be evaluated by counting unused tablets and capsules. Participants will be instructed to bring all unused study drugs to the site at Visit 3 (Day 28) and at Visit 4 (Day 84) (or at an EOT Visit, in cases of early discontinuation of study drug or study). During the Treatment Period, if compliance is not between 80% and 120%, inclusive, the participant will be counselled about the importance of compliance with the regimen.

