8.4 Pregnancy Reporting

If a participant becomes pregnant during the study or within the Safety Follow-up Period defined in the protocol, the Investigator is to stop dosing with the study drug immediately. The participant should complete an EOT Visit as soon as possible. The participant will continue to participate in study visits as described in Section 4.5.

If the female partner of a male participant becomes pregnant while the participant is receiving study drugs or within the Safety Follow-up Period defined in the protocol, the Investigator should notify as described above.

The pregnancy should be followed until the outcome of the pregnancy, whenever possible. Once the outcome of the pregnancy is known, the EIU form should be completed and faxed/emailed to . If the outcome of the pregnancy meets the criteria for immediate classification as an SAE (ie, postpartum complication, spontaneous abortion, stillbirth, neonatal death, or congenital anomaly), the Investigator should follow the procedures for reporting an SAE.

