- b. A participant who is screened and does not meet the study eligibility criteria may be considered for rescreening upon Sponsor and/or Medical Monitor consultation and approval. Rescreened participants will be assigned a new participant number. Rescreening should occur no less than 5 days after the last screening visit.
- c. Participants who discontinue study drug between Visit 2 (Day 1) and Visit 3 (Day 28) or at Visit 3 (Day 28) should complete an EOT Visit at Day 28, return to complete Visit 4 (Day 84), and return to complete the Safety Follow-up Visit (Day 112). In addition, participants who withdraw from the study should complete an EOT Visit. Participants who discontinue study drug between Visit 3 (Day 28) and Visit 4 (Day 84) will not undergo an EOT Visit but continue with study visits per protocol.
- d. Participants will be required to sign an ICF before any study-related procedures are performed.
- e. Confirm the participant continues to meet the inclusion and exclusion criteria and assess any updates since Screening (Visit 1).
- f. Weight and height will be measured at Screening (Visit 1) and will be used to calculate body mass index. Measurement of weight should be performed with the participant dressed in indoor clothing, with shoes removed.
- g. The physical examination should comprise a focused examination, which includes general, respiratory, CV, abdominal, and extremities evaluations.
- h. Vital signs will include body temperature, heart rate, and triplicate blood pressure (systolic and diastolic) measurements. Participants should be in the supine position after at least 10 minutes rest prior to the vital sign measurements.
- i. A single 12-lead ECG will be performed in the supine position after 10 minutes of rest. ECGs are to be assessed for clinical significance by a qualified medical designee at the study site.
- j. For women of childbearing potential only.
- k. FSH test will be performed in women <55 years of age for whom it has been ≥1 year since their last menstrual period.
- 1. At Screening (Visit 1), Visit 4 (Day 84), and EOT, chemistry panel will include HbA1c.

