- s. Study drugs (2 tablets and 1 capsule) will be administered by the participant orally with water, with or without food, once daily on Day 1 to Day 84 at approximately the same time each morning. On days with visits scheduled, participants should not take the study drugs prior to the visit but should bring the study drugs with them to the site. The study drugs will be administered with water following all fasted blood samples. At Visits 3 and 4, participants will dose from the kit received at the previous visit (Visits 2 and 3, respectively). If a participant permanently discontinues study drug, he/she will continue to participate in study visits, as described in Section 4.5, but will no longer administer study drug.

COVID-19 = Coronavirus Disease 2019; CV = cardiovascular; ECG = electrocardiogram; EOT = End of Treatment; FDC = fixed dose combination; FSH = follicle-stimulating hormone; HbA1c = glycosylated hemoglobin; HDL-C = high-density lipoprotein cholesterol; ICF = informed consent form; IRT = interactive response technology; LDL-C = low-density lipoprotein cholesterol; Lp(a) = lipoprotein (a); NMR = nuclear magnetic resonance; PK = pharmacokinetic(s); TG = triglyceride(s); UACR = urine albumin-creatinine ratio; VLDL-C = very low-density lipoprotein cholesterol.

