- q. This assessment does not need to be repeated if the participant discontinued study drug early and has already undergone an EOT Visit.
- r. At Visit 2 (Day 1), participants will receive 1 kit (containing 36 FDC tablets or matching placebo tablets, 36 obicetrapib tablets or matching placebo tablets, and 36 ezetimibe capsules or matching placebo capsules totaling 108 tablets/capsules per kit) with the study drugs appropriate for the participant's treatment group. At Visit 3 (Day 28), participants will receive 2 kits as described above. The 2 kits provide sufficient supplies for 56 days of dosing, with enough for an extra 16 days of dosing in case the participant needs to postpone Visit 4 (Day 84). Each individual kit will provide a sufficient supply for 28 days of dosing, with enough for an extra 8 days of dosing. Participants will be instructed to take 3 units from the kit each day. The kit will be clearly labelled to indicate which tablets and capsule to use on each day. Participants will be instructed to bring all unused study drugs to the site at the next visit.
- s. Study drugs (2 tablets and 1 capsule) will be administered by the participant orally with water, with or without food, once daily on Day 1 to Day 84 at approximately the same time each morning. On days with visits scheduled, participants should not take the study drugs prior to the visit but should bring the study drugs with them to the site. The study drugs will be administered with water following all fasted blood samples. At Visits 3 and 4, participants will dose from the kit received at the previous visit (Visits 2 and 3, respectively). If a participant permanently discontinues study drug, he/she will continue to participate in study visits, as described in section 4.5 of the protocol, but will no longer administer study drug.

COVID-19 = Coronavirus Disease 2019; CV = cardiovascular; ECG = electrocardiogram; EOT = End of Treatment; FDC = fixed dose combination; FSH = follicle-stimulating hormone; HbA1c = glycosylated hemoglobin; HDL-C = high-density lipoprotein cholesterol; ICF = informed consent form; IRT = interactive response technology; LDL-C = low-density lipoprotein cholesterol; Lp(a) = lipoprotein (a); NMR = nuclear magnetic resonance; PK = pharmacokinetic(s); TG = triglyceride(s); UACR = urine albumin-creatinine ratio; VLDL-C = very low-density lipoprotein cholesterol.

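### Protocol section 7.2 tells participants to take study drug at the EOT Visit, which contradicts the no-dosing rule in Appendix A footnote s and, for pregnancy, section 8.4

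*Protocol*

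**What the plan says.** Section 7.2 first states that the PK sample is a trough sample taken before dosing. It then names Visits 2, 3 and 4 and continues: "the EOT Visit, in cases of early discontinuation of study drug or study, participants should take study drug after a trough PK sample". The EOT Visit is therefore written in as a dosing visit, with early discontinuation named as the reason for holding it.

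Three other places bear on that visit:

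- **Appendix A footnote s.** If a participant permanently discontinues, "he/she will continue to participate in study visits, as described in Section 4.5, but will no longer administer study drug". SAP Table 1 (in SAP section 2.2.2) carries the same footnote: "as described in section 4.5 of the protocol, but will no longer administer study drug".
- **Section 8.4, pregnancy.** "the Investigator is to stop dosing with the study drug immediately. The participant should complete an EOT Visit as soon as possible".
- **Section 4.5 and Appendix A footnote c.** A participant who permanently stops drug up to or at Visit 3 has an EOT Visit at Day 28 and then attends Visit 4. Footnote c adds that "participants who withdraw from the study should complete an EOT Visit". It also says: "Participants who discontinue study drug between Visit 3 (Day 28) and Visit 4 (Day 84) will not undergo an EOT Visit".

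**The concern.** The EOT Visit exists because treatment has ended. A body-text instruction to take drug there points the wrong way for the people who attend it. Some will have stopped under the liver-enzyme, creatine kinase or renal rules in sections 8.1.4.1, 8.1.4.2 and 8.1.4.4, and some because of pregnancy.

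Drug may well be at hand. Section 5.5.4 asks participants to return unused supply at the EOT Visit, and section 5.5.3 has them hold the day's dose until the fasted samples are drawn. The documents do not say which text prevails if a coordinator follows section 7.2 and does not reach footnote s. What is at stake is a needless dose in a participant who should have none. No trial result is at stake.

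**Working it through.** No arithmetic applies, and the plan states no figure to reproduce. The check is a comparison of texts, in three steps.

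**1. Who attends an EOT Visit?** The protocol gives three routes: permanent discontinuation up to or at Visit 3 (section 4.5, footnote c), pregnancy (section 8.4), and withdrawal from the study (section 4.5, footnote c). Section 4.5 sets out the Day 28 EOT Visit under its rule for permanent discontinuation. That first group is therefore the same group that footnote s addresses.

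**2. What does each text say about dosing?**

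| Situation | Section 7.2 | Other text | Result |
|---|---|---|---|
| EOT after permanent discontinuation | Dose after the PK sample | Footnote s (Protocol and SAP): no further drug | Direct conflict |
| EOT after pregnancy | Dose after the PK sample | Section 8.4: dosing has already stopped | Direct conflict |
| EOT after study withdrawal | Dose after the PK sample | Footnote s does not name withdrawal | Conflict by implication only |
| Visit 4, participant already off drug | Dose after the PK sample, no exemption repeated | Footnote s supplies the exemption | General rule with its exception stated elsewhere |

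**3. Is the sentence needed to fix the order of sample and dose?** No.

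- The sentence before it in section 7.2 and Appendix A footnote o already place the PK sample before dosing. Neither directs a dose at EOT.
- Section 5.5.3 puts dosing after the fasted blood samples. Where it says which kit to dose from, it names Visits 3 and 4 but not the EOT Visit.
- Section 7.1.6 deals with the serum archive sample at the same EOT Visit and asks only that it be collected before drug.

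At the EOT Visit, then, the only thing the section 7.2 sentence adds is the instruction to dose.

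**The case against.** The best defence is that the sentence concerns sequence. Read after the one before it, it most naturally means that drug must not be taken before the sample. More specific rules then govern whether any drug is taken: footnote s after permanent discontinuation, section 8.4 in pregnancy, and the stopping rules in section 8.1.4. On that reading nobody is dosed in error. As an account of intent this is probably right, and it is why an actual dose is unlikely. It does not remove the conflict, because section 7.2 is not silent about stopped participants. It names early discontinuation and still says to take drug.

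A reader might go further in three directions that the documents do not support.

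- **That section 7.2 also contradicts footnote s at Visit 4.** Participants who stop between Visits 3 and 4 do attend Visit 4 off drug, and section 7.2 does not exempt them. But Visit 4 is an ordinary dosing visit for everyone still on treatment. Section 5.5.3 states the dosing rule equally generally, and footnote s states the same rule and then adds the exception. Leaving an exception unrepeated is normal drafting.
- **That dosing at a withdrawal EOT Visit is expressly forbidden.** Footnote s concerns someone who stops drug and keeps attending visits. Section 4.5 requires study withdrawal to be kept distinct from stopping drug. The purpose of an EOT Visit argues against a dose, but no text says so for this group.
- **That data are compromised.** Any such dose would follow that visit's PK and fasted samples, so those results stand. The Day 84 value enters the primary analysis under a treatment-policy strategy whether or not drug was stopped.

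**Conclusion.** The point holds as a minor wording conflict. One sentence in section 7.2 directs a dose at the EOT Visit. That contradicts footnote s, in both the Protocol and the SAP, for participants who have permanently discontinued, and it contradicts section 8.4 for those who are pregnant. For study withdrawal the conflict is implied only.

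The intended rule, no drug after permanent discontinuation, is already in the documents. What needs correcting is an instruction that departs from it. The safety relevance is small but real, because the affected group includes participants stopped for safety findings or pregnancy.

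No efficacy result, power or type I error changes. The documents give no rate of stopping study drug, so no number of affected participants is claimed. That unused drug may be on site shows only that a dose is possible, not that it is likely. The conclusion assumes that section 7.2 is read as written and that footnote s states the sponsor's intent.

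**What to change.** In section 7.2, delete the EOT Visit from the dosing sentence and state that the EOT PK sample is collected with no dose afterwards. This also settles the withdrawal case. Keep PK sampling at the EOT Visit as scheduled.

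Optionally, for Visits 3 and 4, add that dosing applies to participants still on study drug, with a cross-reference to Appendix A footnote s. This is a clarification only, since footnote s already supplies the exemption.

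The cost is a short edit to section 7.2 and a clarification memo to sites. No new data, procedure or analysis is needed, and the SAP needs no change.
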